Clinical Research Protocol Template version 15.0

© Copyright: The University of Oxford and Oxford University Hospitals NHS Foundation Trust 2019 Page 18 of 113 month. In Phase I and II to date, acceptance of additional visits was very high and therefore follow-up visits are also included in the target of 150,000 individuals sampled every fortnight in England from October 2020 onwards (and equivalently in Devolved Administrations). We will also approach anyone with a positive test for virus (i.e. new infection) in the study to undergo a blood draw as quickly as possible after their positive test and then at monthly visits to contribute additional information to analyses of how immunity after infection changes over time, where this does not lead to targets for blood sampling being exceeded by >5% (which impacts the capacity of the laboratory to conduct all the required tests).

However, in order to monitor the impact of vaccination on both immunity and infection, from February 2021, we will ask a representative sample of those already recruited to the study but only giving swabs to also give blood at their monthly visits, and for everyone giving blood samples to stay in the study until April 2022 (i.e. to have additional visits beyond their original 12 month study period). Blood will initially either be taken through a venous blood draw as previously or through a capillary blood draw (fingerprick) done by the participant. From protocol v9.0, all blood draws will be capillary so that all visits can be conducted without any contact. The blood target from April 2021 to March 2022 is to achieve up to ~125,500 adults 16 years and older with blood test results every month in England, and up to ~7,500, ~4,500 and ~12,500 per month in Wales, Northern Ireland and Scotland (~150,000 in total across the UK) (absolute numbers reflecting the relative size of the underlying populations). Where an adult in the household is already giving blood, in order to monitor the impact of immunity as well as infection in younger individuals, from September 2021 we will also ask children and young people aged 8-15 years whether they would be happy to give a sample of blood (5-7 years in an initial pilot in October 2021 only). See Section 9.4.3 for rationale and details. For those aged 8-15 years, from December 2021 to March 2022, the target is to achieve ~3,600 blood test results from older children/adolescents every month.

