9.4. Enrolment

There is no intervention.

Whether a household is approached for blood sampling is randomly allocated (whether at recruitment or subsequently).

Participants will be enrolled at the first home visit up to protocol v15.0, or at a telephone call at which consent is taken, 16 to 9 days before the first assessment from protocol v16.0.

9.4.1. Post enrolment recruitment into providing monthly blood samples and extending follow-up in those providing blood samples to April 2022 (from protocol v7.0)

A random sample of 10-20% households has been approached for consent to provide blood samples from the point of recruitment for the duration of their follow-up in the study. However, larger numbers are required to assess the impact of vaccine rollout on population level immunity (see Section 11.3 below). Therefore from February 2021, a randomly selected sample of already enrolled households who are currently providing swab but not blood samples, and where at least one person originally provided consent for 12 months' follow-up, will be invited to additionally provide blood samples at their monthly visits and extend their follow-up through to April 2022. This will be optional, and will be on an individual basis in those aged 16 years and older, but will be for both components (follow-up to April 2022 and monthly blood draws). Those aged 16 years or older who do not provide consent for this optional blood sampling will remain on monthly follow-up from the original household recruitment date with swabs only. If anyone in the household provides additional consent, then parents/carers of anyone aged under 16 years in the household will be approached for consent to extend follow-up to April 2022 only for these individuals (to ensure that the household continues follow-up together).

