© Copyright: The University of Oxford and Oxford University Hospitals NHS Foundation Trust 2019 Page 61 of 113 national testing programmes as required, also to enable immediate movement of positive results into the national tracing systems (see Section 12). National tracing systems will then immediately and automatically notify participants of positive results. Participants will be informed about this automatic referral of a limited set of personal data to be linked to test results in the Participant Information Sheet, and that by taking part in this survey they agree to this disclosure taking place. In addition, all results will be returned directly to the participant by email or letter, as described above.

As described above, the household of any participant with a positive nose and throat swab for virus during the study (either from a study sample or from a test result linked to study data from national databases) would also be approached for consent for a blood draw as quickly as possible after the first positive test in the household and then at subsequent monthly visits to the end of their participation, where this does not lead to targets for blood sampling being exceeded by >5% (which impacts the capacity of the laboratory to conduct all the required tests). Consent for blood draws after testing positive on a nose and throat swab within the study will be sought at enrolment, to avoid needing to reconsent individuals. Individuals would be telephoned in order to expedite blood sampling and this would be followed up with a letter. Participants will be informed about this in the Participant Information Sheet.

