11.2. Description of the Statistical Methods

For the primary outcome, Bayesian dynamic spatiotemporal multi-level regression with poststratification (MRP) will be used to investigate changes in positivity rates over calendar time.^{25,26} Potential spatial correlation between neighbouring areas is taken into account using a "BYM2" specification. Time will be allowed to vary in a non-linear fashion by using a first-order autoregressive term for time. Space-time, and space-age interactions will be included to allow the positivity over time to vary by age and age group. This spatiotemporal MRP is an extension of the spatial MRP method developed by Gao et al.²⁷ In extensive simulations, Gao et al found that bias was significantly reduced when using a BYM2 specification compared to a non-spatial independent identically distributed specification. Attenuation in absolute bias was most apparent with small sample sizes. Even when simulating outcome data as a multivariate independent normal, BYM2 spatial prior produced nearly same posterior estimates as independent identically distributed prior, indicating that the BYM2 spatial prior does not force spatial structure when it is not present.

The reason for using MRP as the primary method is because it allows probabilistic assessment of relatively rapid changes in positivity. MRP consists of two steps. First, a multilevel regression model is used to generate the outcome of interest as a function of (socio)demographic and geographic variables. Next, the resulting outcome estimates for each demographic-geographic respondent type are poststratified by the percentage of each type in the actual overall population. In several empirical and simulation studies MRP was superior at both the national and regional levels to classical survey weighted and unweighted approaches, including when using small sample sizes.^{26,28} Factors included in the main models - besides time, space, and a space-time interaction described above – will be sex, age, ethnicity and an age-time interaction. Whether additional interactions are needed will be determined based on the Watanabe-Akaike information criterion.

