In addition, the proportion of individuals with symptomatic and asymptomatic infection (based on PCR of nose and throat swabs) based on the latest result in the last two weeks will be summarised approximately every calendar week from the start of the study, overall and by geographical region. Proportions will be calculated incorporating sampling weights for the original ONS and NISRA surveys, this survey and for non-response to this survey, with 95% confidence intervals estimated using the Korn-Grauberd method which allows for the low anticipated positivity rates. We will use Bayesian methods in sensitivity analyses assessing the impact of plausible ranges of test sensitivity and specificity on results, incorporating both the assay performance and the fact that participants are self-swabbing. Associations between various predictors and ever testing positive for infection vs never testing positive will be estimated using unweighted proportions and Fisher's exact tests with multivariable logistic regression models to adjust for confounding. Factors considered will include sex, ethnicity, age at last birthday (as both categorical and continuous variables) and other responses to the short questionnaire. These factors will also be considered in multi-level regression models, similar to the main model over continuous time described above.

Similar spatiotemporal MRP methods will be used to estimate proportions over time with immunity defined based on the optical density readings from the ELISA assay for IgG antibodies versus the threshold defined in comparison with pre-pandemic plasma. We will also estimate the proportions with previous infection (as defined by antibodies) but no previous symptoms.

Random effects linear regression models will also be generated for the absolute optical density readings (potentially log-transformed depending on the distribution) in relation to time since onset of first symptoms, with those not reporting symptoms treated as an additional category (random effect per household – may be omitted depending on model fit). Additional factors considered in these models will include age, sex and ethnicity.

Incidence will be calculated indirectly by deconvoluting the Bayesian dynamic multi-level regression model estimate of swab positivity and an estimate of duration of PCR positivity based on those testing positive in the study. More details are provided on

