11.4. Analysis populations

All enrolled participants will be included in analyses, which will adjust for clustering by household wherever possible. Secondary analysis will also be conducted de-duplicating to one individual per household, for example restricting to adults targeted by ONS in the original approach letter.

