11.8. Procedure for Accounting for Missing, Unused, and Spurious Data

Each analysis will be restricted to complete cases for the outcomes and exposures considered for that analysis. Missing assay data is expected to be extremely rare, as study workers will oversee the participant self-swabbing of nose and throat, participant capillary blood draw, and ask the specific additional questions at the home visit. From protocol v16.0, samples will be returned predominantly by post, so missing data may increase somewhat, but postal return has been used successfully by other research studies such as REACT and Biobank without substantial amounts of missing data. The RT-PCR and ePCR tests for virus have been used as a diagnostic throughout the pandemic and hence have extremely high performance. Sufficient sera will be obtained to re-run the immunological assays in case of initial assay failure. For similar reasons we do not anticipate that spurious data will be obtained.

Regular checks for data quality will be run on the small amount of predominantly self-reported data collected (see section 9.6.1). Standard range checks and plausibility checks will be run on all data fields as part of routine data processing for interim analyses. For participants agreeing to serial sampling, consistency between visits will also be checked. Given the short-time scales of the study visits, last observation carried forward and backward will be used to impute any missing data.

Standard inverse probability weighting methods or post-stratification will be used to weight observed data back to a representative UK population, based on response to the initial ONS letter in adults originally targeted, their characteristics compared with those to whom the original invite to participate in the ONS and NISRA surveys, and those characteristics vs the general UK population.

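### Households join the blood cohort because a member tested positive, yet the seroprevalence analysis has no term or weight for this route, which biases antibody prevalence upward by an amount that depends on period and marker

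*Protocol*

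**What the plan says.** **Route into blood sampling.** Under Section 9.9.2, the household of a participant with a positive swab "would also be approached for consent for a blood draw as quickly as possible after the first positive test in the household" and then at monthly visits. That section counts positives from study samples and from linked national databases; Section 7 describes the same route for study samples only. Sections 5 and 7 give the purpose, which is to "contribute additional information to analyses of how immunity after infection changes over time". The approach is made "where this does not lead to targets for blood sampling being exceeded by >5" per cent. The footnotes to Figures 2A and 3A, covering the period through v15.0, give the route without that condition.

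**Selection as described elsewhere.** Section 9.4 states: "Whether a household is approached for blood sampling is randomly allocated (whether at recruitment or subsequently". Section 8.4, on blood sampling, does not mention the triggered route.

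**Analysis.** Section 11.4: "All enrolled participants will be included in analyses, which will adjust for clustering by household wherever possible". Section 11.2: "Similar spatiotemporal MRP methods will be used to estimate proportions over time with immunity defined based on the optical density readings". Besides time, space and their interaction, the factors in the main models "will be sex, age, ethnicity and an age-time interaction"; only further interactions are left open. The weights in Section 11.8 are "based on response to the initial ONS letter in adults originally targeted" and on population characteristics. Section 11.1 says that there is no formal statistical analysis plan. Section 11.2 also points to an external methods article, which is not at hand.

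**The concern.** Entry by this route depends on infection, and infection is a cause of the antibody outcome. Post-stratifying by sex, age, ethnicity and area corrects for imbalance in those factors. It does not correct for over-representation of recently infected households within each cell. Weights for response to the invitation letter do not do so either, and adjusting for household clustering affects the precision rather than the selection. Over-sampling of blood households by ethnicity (Section 7) is matched by a model term; over-sampling by infection is not.

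Population immunity and its change over time is a secondary objective in Section 6. The triggered share is likely to follow infection waves, so the trend could be affected as well as the level. A larger sample does not reduce such a bias.

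**Working it through.** **1. The plan's own precision, as a yardstick.** Section 11.3 aims at a margin of error below 2% for a region with about 10,000 to 15,000 blood results per month, and defines the margin as the full width of the exact 95% interval. At 50% prevalence the exact width is 1.97 points for n = 10,000 and 1.61 for n = 15,000, so the stated figure reproduces. The half-width is 0.99 to 0.80 points. At 10% prevalence it is smaller: 1.96 × √(0.10 × 0.90 / 10,000) = 0.59 points.

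**2. Formula.** Let f be the triggered share of blood results, s the seropositivity in triggered households and π that in randomly invited households. The pooled proportion is (1 − f)π + f s, which differs from π by f × (s − π). This holds within any post-stratification cell. The documents give neither f nor s, so what follows is a range under assumptions.

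**3. Anti-S at the standard threshold, recent period.** Section 9.6.1 gives more than 97% positive. Since s cannot exceed 100%, the bias is at most 3 points × f. If triggered draws were only the permitted 5% excess over target, f = 0.05 / 1.05 = 4.8%, and the bound is 0.0476 × 3 = 0.14 points.

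**4. Low prevalence.** Assume π = 10% and s = 60%.

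| f | f × (60% − 10%) |
|---|---|
| 1% | +0.5 points |
| 2% | +1.0 points |
| 4.8% | +2.4 points |
| 10% | +5.0 points |

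An f of 2% is enough to match the regional half-width in step 1. That half-width belongs to the enlarged cohort of 2021–22. When fewer people gave blood, sampling error was larger, so it serves as a scale and not as a same-period comparison.

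**5. Could f be that large?** Until January 2021 only 10–20% gave blood (Synopsis). With r the random blood fraction, c the share of swab-only households with a positive and u the uptake, f = c(1 − r)u / [r + c(1 − r)u].
- r = 20%, c = 1%, u = 50%: 0.004 / 0.204 = 2.0%.
- r = 10%, c = 5%, u = 100%: 0.045 / 0.145 = 31%.

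The values of c and u are assumptions. The point is only that a few per cent is easily reached when the random blood cohort is small.

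**6. The 5% condition is not a bound on f.** It limits how far total blood samples may exceed the laboratory target. If the random cohort falls short of target, triggered households can fill the gap and f can exceed 4.8%.

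**7. Later random invitations.** From February 2021, Section 9.4.1 invites households giving swabs but not yet blood. Households already triggered have left that pool, so those invited later are slightly depleted of past infection. This partly offsets the bias in step 2. The net direction stays upward as long as households with a positive are more likely to end up in the blood cohort than those without.

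**The case against.** The strongest counter-case has four parts.

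- **Size.** A reader might combine the 5% condition with low prevalence and a high seropositivity, for example 4.8% × (85% − 10%) = 3.6 points, and treat that as the bias. The documents do not support this. Appendix II logs the 5% condition at v15.0, between v14.0 (December 2021) and v16.0 (March 2022), when anti-S positivity at the standard threshold already exceeded 97%. Nor is 85% supported: the whole household is approached, including uninfected members. The Lay Summary says antibodies take 2–3 weeks to develop, so a rapid first draw may precede seroconversion. This objection stands.
- **Other markers.** The documents give no prevalence for anti-N or for the 179 ng/mL threshold, and from v16.0 anti-N is assayed only in a subset. A firm figure for either would be speculation. This stands; that they may be further from the ceiling is all that can be said.
- **Reading of the analysis text.** Section 11.4 is a general sentence, Section 11.2 says similar rather than identical methods, and the triggered samples have a stated purpose. That leaves room for an unstated restriction in practice, so a reader should not conclude that published estimates are known to be materially wrong. But the purpose is not written as a limit on use, and the only stated population is all enrolled participants.
- **The contradiction is minor.** Table 2A separates the random and triggered routes, so the route is disclosed. True, but the sentence in 9.4 covers approaches after recruitment and is wrong as it stands.

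**Conclusion.** The concern holds, with a size that varies by period and marker. Entry to blood sampling depends partly on infection, which contradicts Section 9.4, and the stated analysis population, model terms and weights do not account for it. Following the plan as written biases seroprevalence upward by f × (s − π), given that triggered households are more often seropositive than randomly invited ones.

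For anti-S at the standard threshold in the recent period the effect is negligible: at most 3 points × f, or about 0.14 points at f = 4.8%. At low prevalence it could exceed the regional half-width of about 1 point: with π = 10% and s = 60%, both assumed, f above about 2% does so. It may matter for anti-N and the 179 ng/mL threshold, but the documents do not allow a figure. Because the objective is the course of immunity over time, the small recent effect does not settle the matter for the whole series.

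**What to change.** - **Sections 11.2 and 11.4.** Flag each participant's route into blood sampling. Weight the seroprevalence estimates by the probability of blood selection given prior household positivity, which can be estimated from the full enrolled swab cohort.
- **Alternative.** Restrict seroprevalence estimates to households randomly invited at enrolment. If those from the later random invitation are added, correct for triggered households no longer being eligible for it. Simply dropping triggered households is not clean, because it leaves the later-invited group short of past infections and so tends to bias downward.
- **Antibody-response models.** Keep the triggered samples in full; that is their stated purpose.
- **Section 9.4.** State that approach for blood is random except for the positivity-triggered route, mention that route in 8.4, and reconcile Sections 7 and 9.9.2 on whether linked national results count as a trigger.

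The cost is modest extra analysis and some loss of effective sample size in the seroprevalence estimates. The documents do not say whether the entry route is already recorded as a field, so it may have to be derived from consent and invitation records.

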9.9.3 Pilot community respiratory surveillance

Given the lack of circulating other respiratory viruses, influenza in particular, since the start of the COVID-19 pandemic in 2020, there is considerable concern about the potential for substantial morbidity due to influenza and other respiratory viruses in the Autumn and Winter of 2022/23. Current influenza surveillance is predominantly syndromic, testing symptomatic adults presenting to specific general practices in the Royal College of General Practitioners network every week. There is no representative community surveillance including asymptomatic individuals (estimated to comprise approximately 14% of cases in the Fluwatch study) or children.

From September 2022, in order to provide initial information on community circulation of respiratory pathogens, a pilot community respiratory surveillance study will be nested within the CIS. Every week, around 750 residual pathogen RNA extracts from randomly selected nose and throat swabs will be sent, after testing for SARS-CoV-2 testing, for additional testing for influenza and potentially RSV. A random selection of assay plates will be made at the laboratory on one day of each week and shipped for testing. This is feasible and should provide an approximately random selection of survey participants, including symptomatic and asymptomatic and across age groups and regions. Samples are only identified at the laboratory by barcodes so it is not possible to stratify sample selection by any participant characteristics such as age or region. Depending on capacity, tests will either be done at the Rosalind Franklin Laboratory using the TaqPath™ COVID-19, FluA/B, RSV Combo Kit or at the UKHSA laboratories at Colindale using an influenza multiplex assay identifying sub-types A/H1/N3/B, basarrive ed on primers/probes designed in house. As only a very small number of the ~69,500 swab samples taken each week will be tested within this pilot (~750, ~1%), and these will be from a completely random set of participants, different each week, and because the expectation is to find very few positive results (see below), results of these additional tests will not be returned to participants. Results of standard SARS-CoV-2 testing will be returned as normal.

The primary goal of this pilot study is to identify a tipping point of community influenza prevalence such that in ~2-3 weeks time, hospitals will start to see substantial numbers of cases. Testing 750 samples and observing zero influenza cases provides an estimate of community prevalence of 0% with a 95%

confidence interval up to 0.5%, allowing us to rule out virus circulating in more than 0.5% of the community. Testing a smaller number of 400 samples per week for RSV (laboratory dependent) would provide an upper 95% confidence interval of 1%, allowing us to rule out virus circulating in more than 1% of the community. If positives are observed, estimates may be provided by age and other characteristics depending on numbers. Extracted viral RNA will be sequenced for all positives, in order to provide early information on circulating variants in order to assess congruence with the winter season's flu vaccine components.

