In most settings, laboratory diagnosis of infection has been based on real-time reverse transcriptase polymerase chain reaction (RT-PCR). Diagnostic RT-PCR typically targets the viral ribonucleic acid (RNA)-dependent RNA polymerase (RdRp) or nucleocapsid (N) genes using swabs collected from the upper respiratory tract (nose and throat).^{6,7} However, the requirement for specialist equipment, skilled laboratory staff, and PCR reagents has created bottlenecks. Clinical care and public health containment efforts are thus impeded by diagnostic delays even for clinically unwell patients, and further limited by a lack of wider testing including both mass screening, and specific high-risk groups (contacts of confirmed cases, and healthcare workers and their families). Further the numbers who are asymptomatically infected are currently completely unknown. Poor population-level data adds uncertainty to dynamic models that inform planning of lockdown restrictions (as exemplified by experiences in other countries⁸). Furthermore, even when available, RT-PCR from upper respiratory tract swabs may be falsely negative, due to quality or timing of collection; viral titres in upper respiratory tract secretions peak in the first week of symptoms,⁹ but may have declined below the limit of detection in patients who present with symptoms beyond this time frame.¹⁰ In individuals who have been infected and recovered, RT-PCR provides no information about prior exposure or immunity.

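### The influenza and RSV limits of 0.5% and 1% in section 9.9.3 bound swab positivity; they bound infection in the community only if detection is near perfect

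*Protocol*

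**What the plan says.** Section 9.9.3 of the protocol describes a weekly pilot that tests residual RNA extracts from about 750 randomly selected swabs for influenza and possibly RSV. If none of the 750 is positive for influenza, the protocol takes the estimate to be zero and the upper limit to be half a per cent, and describes this as "allowing us to rule out virus circulating in more than 0.5" per cent of the population. For RSV the number is 400 a week, which "would provide an upper 95% confidence interval of 1%, allowing us to rule out virus circulating in more than 1% of the community".

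Section 6 lists prevalence of other respiratory infections as an exploratory objective. Its outcome measure is whether another respiratory virus is detected on the same nose and throat swab used for SARS-CoV-2.

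Two other places concern missed infections, both written about SARS-CoV-2. Section 5 accepts that "RT-PCR from upper respiratory tract swabs may be falsely negative, due to quality or timing of collection". Section 11.2 plans Bayesian sensitivity analyses over plausible test sensitivity and specificity, "incorporating both the assay performance and the fact that participants are self-swabbing". Section 9.9.3 gives no sensitivity for influenza or RSV and makes no allowance for missed infections.

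**The concern.** A zero count bounds the probability that a sampled swab tests positive. Section 9.9.3 words the result as a bound on virus circulating in the community, which is a statement about infection. The two agree only if essentially every infected participant tests positive. The pilot uses the same participant-taken or parent-taken swabs that the protocol elsewhere treats as imperfect, and the influenza figure has almost no room before it passes 0.5%.

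At stake is how a zero week is read. These limits are the only precision figures given for the pilot, since section 11.3 does not cover it. The pilot's stated goal is to spot the level of community influenza that precedes hospital cases by about 2 to 3 weeks. A reader who takes 0.5% as a limit on infection would be somewhat more reassured than the data allow.

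**Working it through.** **Inputs from the protocol.** Section 9.9.3: n = 750 with zero positives and a stated limit of 0.5% (influenza); n = 400 with a stated limit of 1% and a zero count implied (RSV). Section 11.3: exact binomial 95% intervals are the method used for the main survey. Samples are treated as independent, as the stated limits require.

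**Input not in the documents.** Sensitivity (Se) of the whole swab-to-result process for influenza or RSV. It is taken below as an assumed range, with specificity 1.

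**Step 1: reproduce the stated limits.** With zero events the exact two-sided 95% upper limit is 1 − 0.025^(1/n).

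- n = 750: 0.491%, stated as 0.5%.
- n = 400: 0.918%, stated as 1%.

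The one-sided 95% limit, 1 − 0.05^(1/n), gives 0.399% and 0.746%, which do not match the stated figures. The protocol's limits are therefore the two-sided ones, with no sensitivity term.

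**Step 2: convert to infection.** With specificity 1, positivity = Se × prevalence, so the upper limit for infection = [1 − 0.025^(1/n)] / Se.

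| Assumed Se | Influenza, n = 750 | RSV, n = 400 |
|---|---|---|
| 100% | 0.491% | 0.918% |
| 95% | 0.516% | 0.966% |
| 90% | 0.545% | 1.020% |
| 80% | 0.613% | 1.147% |
| 70% | 0.701% | 1.311% |

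**Step 3: sensitivity at which each claim just holds.**

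- Two-sided: 0.4906/0.5 = 98.1% (influenza); 0.918/1 = 91.8% (RSV).
- One-sided: 0.3986/0.5 = 79.7% (influenza); 0.746/1 = 74.6% (RSV).

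**Step 4: chance of a zero count when prevalence equals the stated level,** (1 − Se × p)^n.

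- Influenza, p = 0.5%: 2.3% at Se = 100%; 4.9% at Se = 80%.
- RSV, p = 1%: 1.8% at Se = 100%; 4.0% at Se = 80%.

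**The case against.** The strongest reply is that nothing is miscalculated and that the protocol defines its outcome as virus detected on the swab. Section 6 says so for this objective, and the precision calculations in section 11.3 are likewise plain binomial. On that reading, 0/750 bounds exactly what the pilot estimates. This stands as far as the arithmetic and the outcome definition go. It does not rescue the wording in section 9.9.3, which moves from the tested samples to what is circulating in the community.

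A second reply is that ruling out a higher level is naturally a one-sided claim, and one-sided limits survive down to about 80% and 75% sensitivity. Rounding also absorbs part of the shift: 0.516% and 0.545% still read as 0.5%. Both points are fair and show that the effect is modest, although the limits the protocol quotes are the two-sided ones.

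Third, section 5 and section 11.2 concern SARS-CoV-2 and say nothing about how well influenza or RSV is detected. That is correct, and it is why the size of the effect can only be shown over an assumed range. The high assay performance asserted in section 11.8 also refers to the SARS-CoV-2 tests, so it does not settle the matter the other way.

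A reader might infer more: that with any imperfect swab a zero count fails to exclude these levels, or that the plan would wrongly declare the viruses absent. The documents do not support either. RSV at 1% is still excluded at 95% sensitivity (0.97%). Section 9.9.3 reports an upper limit, does not declare absence, and ties no action to 0.5% or 1%.

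**Conclusion.** The point holds as one of interpretation, and its size is modest. The 0.5% and 1% figures are correct limits on swab positivity. As limits on infection in the community they hold, on the protocol's own two-sided basis, only if sensitivity is at least 98.1% for influenza and 91.8% for RSV. Over an assumed sensitivity of 95% to 70% the infection limits are about 0.52% to 0.70% and 0.97% to 1.31%.

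This rests on independent samples, specificity of 1 and an assumed sensitivity range, because the documents give no value for either virus. It does not show that the pilot is too small or that any decision in the plan would change. It is not a detail awaiting a separate analysis plan: section 11.1 says there is no formal one, and the issue is what section 9.9.3 states.

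**What to change.** In section 9.9.3:

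- Describe 0.5% and 1% as upper 95% limits on the proportion testing positive on a swab.
- Add that the corresponding limit on infection is 0.49% divided by sensitivity for influenza and 0.92% divided by sensitivity for RSV. Show the range for an assumed 95% to 70% (about 0.52% to 0.70% and 0.97% to 1.31%), labelled as an assumption.

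In section 11.2, state that the planned Bayesian analysis of test sensitivity and specificity also applies to the influenza and RSV results.

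The cost is a few sentences and one extra analysis of a kind already planned for SARS-CoV-2. The stated limits become slightly less favourable. No change to the number of samples is needed.
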